Investigator Studies Program Review Committee (MISP-RC)

IIS Clinical Concept Form

All fields are required, an incomplete form will be returned to the submitter. If a field is not completed, please note the reason.

Proposed Study Title

| | |
|---------------|---|
| Study Title: | The effect of glucagon on rates of hepatic mitochondrial oxidation and pyruvate carboxylase flux in man assessed by Positional Isotopomer NMR Tracer Analysis (PINTA) |
| Request Date: | July 1, 2019 |

Principal Investigator Contact Information

| | |
|---------------|--|
| Names: | [name] [name]. |
| Title: | Professor of Medicine |
| Address 1 | Yale University School of Medicine |
| Address 2 | [name] |
| City, ST, Zip | [name] |
| Phone/Fax: | [contact] |
| E-mail: | [contact] , |

Institution Contact Information

| | |
|---------------|---|
| Name: | [name] |
| Address 1 | Office of Sponsored Projects |
| Address 2 | [name] |
| City, ST, Zip | [name] |
| Phone/Fax: | [contact] |
| website | https://your.yale.edu/research-support/office-sponsored-projects |

Contracting Information (if applicable)

| | |
|-------|-----|
| Name: | N/A |
|-------|-----|

Study Information

| | |
|---------------------|-----|
| Indication | N/A |
| Phase: | N/A |
| Number of Subjects: | 12 |

Background and Rationale

- Provide background on unanswered question(s) the study is attempting to answer (do not exceed one page)

While it is well-established that alterations in the portal vein insulin/glucagon ratio play a major role in causing dysregulated hepatic glucose metabolism in type 2 diabetes (T2D), the cellular and molecular mechanisms by which glucagon promotes alterations in hepatic glucose production and mitochondrial oxidation remain poorly understood. This is borne out by the fact that both glucagon agonists and glucagon antagonists are being developed to treat T2D, with unclear mechanisms of action.

Glucagon has long been considered to be one of the major drivers of hyperglycemia in T2D, and glucagon-blocking therapies have been pursued as adjuncts to therapy for both type 1 and type 2 diabetes. Glucagon antagonism using either antibodies against glucagon or its receptor, small molecule antagonists of the glucagon receptor, and antisense oligonucleotides to knock down expression of the glucagon receptor have all shown promising glucose-lowering effects in humans and in animal models of T2D. However, concerns have been raised regarding the potential of these agents to increase liver enzymes by an unknown mechanism. Conversely, a dual glucagon-like peptide-1/glucagon receptor agonist has recently been shown in rodents and non-human primates to lower blood glucose concentrations, associated with increased energy expenditure and weight loss. Taken together, these data suggest a potential role for glucagon to promote hepatic mitochondrial fat oxidation and suggest that a lack of glucagon action may suppress hepatic fat oxidation and predispose to ectopic hepatic lipid accumulation and non alcoholic fatty liver disease (NAFLD).

The impact of glucagon on hepatic mitochondrial oxidative metabolism in humans is unknown but previous studies have suggested a capacity for glucagon to increase liver fatty acid metabolism *in vitro*, and to stimulate hepatic fat oxidation in awake dogs. As predicted by these data, multiple investigators have observed increases in CO₂ generation, O₂ consumption, and activity of the respiratory transport chain in response to glucagon stimulation, consistent with increased mitochondrial tricarboxylic acid (TCA) cycle flux; however, the mechanism by which glucagon stimulate hepatic mitochondrial oxidation and its impact on hepatic mitochondrial oxidation *in vivo* are unknown. In addition we will assess the effects of a physiological increase in plasma glucagon concentrations on rates of hepatic ketogenesis assessed by an infusion of ¹³C₄ β-OHB (Perry et al. **Cell Metabolism** 2017). We have recently shown that allosteric regulation of pyruvate carboxylase by changes in hepatic acetyl-CoA is a key mechanism by which insulin (Perry et al. **Cell** 2015) and glucagon (unpublished results) regulate hepatic gluconeogenesis and that rates of β-OHB turnover are an excellent non invasive surrogate for hepatic acetyl-CoA content (Perry et al. **Cell Metabolism** 2017).

This proposal will directly assess the effect of glucagon on rates of hepatic mitochondrial oxidation and pyruvate carboxylase flux in humans for the first time using Positional Isotopomer NMR Tracer Analysis (PINTA) (Perry et al. **Nature Communications** 2017). The results of these studies have important implications for the possibility of intervening in the pathogenesis of NAFLD-associated hepatic insulin resistance and T2D via chronic dual glucagon-like peptide-1/glucagon receptor agonism and provide an important rationale for why a dual agonist might be more efficacious for treating NAFLD/NASH/T2D than GLP-1 alone.

Objectives

- List the objectives to correspond directly with the listed hypotheses:

To examine the effects of glucagon on hepatic glucose and fat metabolism *in vivo*, we plan to apply a novel Positional Isotopomer NMR Tracer Analysis (PINTA) method to quantify rates of hepatic mitochondrial oxidation (V_{CS}) and pyruvate carboxylase flux (V_{PC}), which has been cross-validated in awake rodents and humans (Perry et al. **Nature Communications** 2017). In preliminary rodent studies we have found that glucagon stimulates intrahepatic lipolysis through an $InsP_3R$ -I-dependent process, leading to increases in hepatic acetyl-CoA content, which allosterically activates pyruvate carboxylase activity and flux (V_{PC}), and that this phenomenon explains its acute, transcription-independent effect to acutely stimulate hepatic gluconeogenesis *in vivo* (unpublished results). In addition, using PINTA analysis we found that glucagon stimulates hepatic mitochondrial oxidation (V_{CS}) through $InsP_3R$ -I-mediated calcium signaling in awake mice, and that this process can be exploited by short-term continuous glucagon treatment leading to two-fold increases in hepatic mitochondrial fat oxidation (V_{FAO}), which in turn results in large reductions in hepatic steatosis and marked improvements in glucose tolerance through reversal of hepatic insulin resistance in a high fat fed rat model of NAFLD.

Hypothesis

- List the clinical Hypotheses in order of priority:

1. A physiological increase in plasma glucagon concentrations will promote a significant increase in rates of hepatic mitochondrial oxidation (V_{CS}) in healthy humans.
2. A physiological increase in plasma glucagon concentrations will promote a significant increase in rates of hepatic pyruvate carboxylase flux (V_{PC}) in healthy humans.
3. A physiological increase in plasma glucagon concentrations will promote a significant increase in rates of $^{13}C_4$ β -OHB turnover (hepatic ketogenesis) in healthy humans.

Study Design/Clinical Plan

- Provide a concise overview stating the type of experimental design

The effects of a physiological increase in plasma glucagon on rates of hepatic mitochondrial oxidation and pyruvate carboxylase flux will be examined in 12 healthy subjects (ages 21-65) using Positional Isotopomer NMR Tracer Analysis (PINTA) (Perry et al. **Nature Communication** 2017). Briefly rates of hepatic mitochondrial oxidation (V_{CS}) and hepatic pyruvate carboxylase flux (V_{PC}) will be assessed in 12 healthy overnight fasted subjects by PINTA after a three-hour infusion of glucagon or saline. The glucagon infusion [3 ng/(kg-min)] will be designed to increase peripheral and portal vein plasma glucagon concentrations 3-4 fold. The effects of a physiological increase in plasma glucagon on rates of hepatic ketogenesis will also be assessed using an infusion of $^{13}C_4$ β -OHB (Perry et al. **Cell Metabolism** 2017).

Rates of hepatic pyruvate carboxylase flux (V_{PC})/citrate synthase flux (V_{CS}) by PINTA: Subjects (n=12) will be studied by PINTA under 2 conditions: 1) at 0700 following an overnight (12h) fast and a 3h saline infusion (Control), 2) at 0700 following an overnight (12h) fast and a 3h glucagon infusion @ [3 ng/(kg-min)] (Glucagon Rx). Briefly, on the morning of the study an IV line will be inserted into an antecubital vein for infusions and second IV line will be inserted retrogradely into a hand vein for blood collections. The hand will be warmed in a 'hot box' to arterialize the blood. After collection of baseline blood samples a 3h infusion of tracers as described below will be started. Relative rates of V_{PC}/V_{CS} will be assessed using a constant

infusion of [$3-^{13}\text{C}$] lactate (8.7 $\mu\text{mol}/[\text{Kg}\cdot\text{min}]$, 99% APE) and rates of glucose production will be measured using a primed/constant infusion of [2H_7]glucose (42 mg/m^2 - 0.84 $\text{mg}/[\text{m}^2\cdot\text{min}]$, 99% APE) (Perry et al. *Nature Communication* 2017). Rates of hepatic ketogenesis will be measured using a constant infusion of [$^{13}\text{C}_4$]βOHB [10 $\mu\text{g}/(\text{Kg}\cdot\text{min})$, 99% APE] as previously described (Perry et al. *Cell Metabolism* 2017). This protocol has been approved the Yale Human Investigation Committee (#20997).

GC/MS Method for Quantifying [$^{13}\text{C}_4$]β OHB turnover: Analysis of the ^{13}C -enrichment in βOHB will be performed by GC-MS. Samples (100 μL plasma) will be dried under N_2 gas and derivatized with 200 μL n- butanol 4N HCl, then heated for 60 min at 65°C and dried under N_2 gas. The samples will next be reacted with 100 μL of trifluoroacetic acid (Thermo Fisher Scientific)-methylene chloride (Sigma) (1:7). [$^{13}\text{C}_4$]βOHB enrichment will be measured by GC-MS (CI mode, m/z 257 [m+0] and 261 [m+4]).

Whole body energy expenditure, VO_2 , VCO_2 , respiratory quotient assessed by indirect calorimetry: Rates of total-body glucose and lipid oxidation and energy expenditure will be calculated from rates of O_2 consumption and CO_2 production measured during continuous indirect calorimetry.

This trial is registered at CT.gov: NCT 03965130

References

Treatment

- List the clinical dosage/dosage form, route, and dose regimen:

Glucagon will be infused intravenously at rate of 3 ng/(kg·min) for three hours.

Collateral Research

- Include biomarkers, PK, etc.

Plasma samples will be collected at the end of each infusion study and banked for future metabolomic analyses to determine if any plasma metabolites track with glucagon-stimulated rates of hepatic mitochondrial oxidation and/or pyruvate carboxylase flux.

Statistical Plans

- Include justification for clinical sample size and primary hypothesis testing:

A group size of 12 subjects was determined based on power calculations to detect a moderate to large difference in the effects of glucagon on rates of hepatic mitochondrial oxidation (V_{CS}). The key endpoints will be to determine if glucagon treatment results in significant differences in: 1) rates of hepatic mitochondrial oxidation, 2) rates of hepatic pyruvate carboxylase flux (V_{PC}), 3) rates of hepatic glucose production, and 4) rates of hepatic β-OHB turnover. Statistical differences in these

parameters (within the same individuals) for saline vs. glucagon treatment will be assessed by paired t-tests.

Budget Summary

- Please be sure to complete budget template (excel document)

| | |
|---|---|
| Total Amount Requested: (Include overhead) | \$1,295,423 (including 30% Yale overhead) |
| Additional sources of funding required? (Yes/No) If Yes, please be specific. | No |

Timelines and Study Plans

| | |
|-------------------------------------|---|
| Number of Sites: | 1 |
| Site Names: | Yale Center for Clinical Investigation, Hospital Research Unit |
| Study Start Date: | July 1, 2019 |
| Study End Date: | June 30, 2020 |
| Number of Subjects: | 10 |
| First Patient In Date: | July 1, 2019 |
| Last Patient Out Date: | May 30, 2020 |
| Enrollment Period in Months: | 11 |

Publication Plan

| | |
|---|--|
| Where are you planning to submit for publication? (journals, etc): | Cell Metabolism, Journal of Clinical Investigation, Nature Medicine, PNAS |
| Are you planning to present your data at a scientific meeting? | |
| Please list your target date for submission of publication. | Approximately 2020 |

Drug Supply Information

| | |
|--|-------------------------------|
| Drug Supplies Required (Yes/No)? | No |
| List Drug Supplies and Amount Required: | Drug Name: Amount: |
| List Drug Supplies and Amount Required: | Drug Name: Amount: |
| Placebo Required (Yes/No)? | No |

| | |
|---|----|
| Additional Sources of Drug Supply (Yes/No). If Yes, please specify | No |
|---|----|

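### The order of the saline and glucagon visits is not stated, randomised or balanced, and the paired t-test has no period term, so a visit effect could be read as a glucagon effect

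*Combined protocol and SAP*

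**What the plan says.** Study Design/Clinical Plan describes a within-subject comparison. It lists the control condition, "Subjects (n=12) will be studied by PINTA under 2 conditions: 1) at 0700 following an overnight (12h) fast and a 3h saline infusion (Control"), and then the active one, "2) at 0700 following an overnight (12h) fast and a 3h glucagon infusion". The overview earlier in the same section has the measurements made "by PINTA after a three-hour infusion of glucagon or saline", which gives no order either.

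Statistical Plans sets out one analysis for all four key endpoints (hepatic mitochondrial oxidation, pyruvate carboxylase flux, glucose production and β-OHB turnover): "parameters (within the same individuals) for saline vs. glucagon treatment will be assessed by paired t-tests".

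The form does not mention sequence, randomisation, counterbalancing, the interval between the two studies, or a period or visit term.

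**The concern.** Both conditions start at 0700 after a 12-hour fast and last three hours, so one morning cannot hold both. The document does not say that there are two study days, but it follows. Each paired difference is therefore also a difference between two visits.

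The plan as written allows any order, including saline first for everyone, which is one reading of the numbered list. In that case visit and treatment coincide exactly, and the conclusion that glucagon raises mitochondrial oxidation rests on assuming that nothing else changed between visits. An order that is mixed but unequal leaves part of the bias. A balanced order removes the bias, but the plain paired t-test then leaves the visit effect in its error term and loses power.

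All four key endpoints depend on this one contrast. A fixed order cannot be repaired once the data are collected.

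**Working it through.** **Inputs from the document.** 12 subjects, two conditions each, paired t-test. The timeline table under Timelines and Study Plans gives 10 subjects; that is a separate inconsistency, and 12 is used here.

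**Assumptions.** Two-sided alpha 0.05, no dropout, and an additive visit effect *d* (second visit minus first), in units of the SD of the paired difference within a sequence. The document gives none of these.

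**The plan's own figure.** Statistical Plans says: "A group size of 12 subjects was determined based on power calculations to detect a moderate to large difference in the effects of glucagon". It gives no alpha, power, SD or numerical effect, so 12 cannot be reproduced. Under the assumptions above, 12 pairs detect a standardised difference of 0.889 with 80% power, and power at 0.8 is 71.4%.

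**Step 1: bias.** Let *k* of the 12 subjects have saline first. Their glucagon-minus-saline difference contains +*d*; for the other 12 − *k* it contains −*d*. The mean paired difference is therefore shifted by

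*d* × [*k* − (12 − *k*)]/12 = *d* × (2*k* − 12)/12.

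- *k* = 12: (24 − 12)/12 = 1, the whole visit effect
- *k* = 9: (18 − 12)/12 = 0.5, half of it
- *k* = 6: (12 − 12)/12 = 0, none

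**Step 2: chance of a significant plain paired t-test when glucagon has no effect.** For 12/0 this is a noncentral t probability with 11 df and noncentrality *d*√12; for example *d* = 0.5 gives 0.5 × 3.464 = 1.73 and a probability of 0.353. The 9/3 and 6/6 rows were simulated (1,000,000 trials for each 9/3 entry).

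| Saline first / glucagon first | *d* = 0.25 | *d* = 0.5 | *d* = 1.0 |
|---|---|---|---|
| 12/0 | 12.4% | 35.3% | 88.3% |
| 9/3 | 6.2% | 9.2% | 15.1% |
| 6/6 | 4.4% | 3.0% | 0.6% |

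At *d* = 0 every row is 5%. For smaller effects with saline always first, the figures are 6.2% at *d* = 0.1, 9.7% at 0.2 and 15.8% at 0.3.

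**Step 3: a visit effect in the opposite direction.** With saline always first and a true standardised difference of 0.889, power falls from 80% to 52% for *d* = −0.25 and to 23% for *d* = −0.5. A fixed order can hide a real effect as well as create a false one.

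**Step 4: what the period term does.** Power at a true standardised difference of 0.8:

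| Order and analysis | *d* = 0 | *d* = 0.25 | *d* = 0.5 | *d* = 1.0 |
|---|---|---|---|---|
| 6/6, plain paired t-test | 71.4% | 69.0% | 62.0% | 37.8% |
| 6/6, with period term (10 df) | 70.5% | 70.5% | 70.5% | 70.5% |

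With the period term and a 6/6 order, type I error stays at 5.0%.

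At 9/3 the period-adjusted standard error is √[(1/9 + 1/3)/4] = √(1/9) = 0.333 SD, so the noncentrality is 0.8/0.333 = 2.4 and power with 10 df is 58%. At 12/0 the term cannot be estimated.

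**Step 5: simple coin tossing.** The chance that unrestricted randomisation of 12 subjects gives a split of 9/3 or more unequal, in either direction, is 2 × (1 + 12 + 66 + 220)/4096 = 598/4096 = 14.6%. Balance should therefore be built into the list.

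**The case against.** The strongest reply is that this shows an omission and not a bias. The form asks only for a concise overview, and it refers to an approved institutional protocol that may set the order. The numbered list need not be a schedule. Under a balanced order the planned t-test is unbiased and its type I error does not exceed 5%. Clock time, fasting and infusion length are matched, the endpoints are tracer-based fluxes and not subjective scores, and nothing in the document points to a visit effect of any given size.

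Much of this stands. The size of the visit effect is assumed, and saline-always-first is a possibility and not a stated fact. Matched conditions narrow a visit effect. The period term is the lesser part of the point: with 6/6 it gains about 1.5 percentage points of power at 0.25 SD (70.5% against 69.0%) and costs 0.9 points if there is no visit effect.

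It does not remove the main issue. Matching does not exclude drift in assay batch, season or body weight between visits. That a fixed order makes visit and treatment inseparable needs no assumed size. On the documents available, nothing prevents such an order.

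**Conclusion.** The concern holds and should be fixed. With high confidence, the document neither states nor balances the order of the two conditions and plans no period term. How much harm follows depends on two unknowns, the order actually used and the visit effect. With saline always first, a visit effect of 0.2 to 0.5 SD of the paired difference raises the false-positive rate from 5% to between 10% and 35%. At 9/3, effects of 0.25 to 1.0 SD give 6% to 15%. At 6/6 there is no bias, only lost power if the period term is left out. These figures assume 12 complete pairs, two-sided alpha 0.05 and an additive visit effect.

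**What to change.** - State the order of the two studies and the interval between them.
- Randomise the order in balance, six subjects saline-first and six glucagon-first, using a list that enforces the split.
- Analyse each key endpoint with treatment and period terms: a mixed model with treatment and period fixed and subject random, or equivalently a two-sample t-test comparing the period differences between the two sequences.
- If the approved institutional protocol already sets a balanced order, state it here and add the period term.

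The cost is a randomisation list, a few lines of text and one degree of freedom. No subjects or visits are added. If there is no visit effect, power at a standardised difference of 0.8 goes from 71.4% to 70.5%, and the difference detectable with 80% power goes from 0.889 to 0.898. The change must be made before the first study day, because a fixed order cannot be corrected in the analysis.

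### Does it matter that the plan does not tie the 3 h glucagon/saline infusion to the 3 h tracer infusion, or name the samples behind each paired t-test?

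*Combined protocol and SAP*

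**What the plan says.** The Study Design/Clinical Plan section says that V_CS and pyruvate carboxylase flux (V_PC) are assessed "after a three-hour infusion of glucagon or saline". It gives the two conditions in matching terms: "1) at 0700 following an overnight (12h) fast and a 3h saline infusion (Control") and "2) at 0700 following an overnight (12h) fast and a 3h glucagon infusion". It then describes placing the lines and adds: "After collection of baseline blood samples a 3h infusion of tracers as described below will be started". For the glucose tracer, "rates of glucose production will be measured using a primed/constant infusion of" labelled glucose, with a prime of 42 mg/m² and a rate of 0.84 mg/m²/min. The lactate and β-OHB tracers are described as constant infusions, with no prime mentioned.

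The Treatment section gives glucagon three hours and says nothing about tracers. Apart from baseline, the only sampling time in the document is under Collateral Research: "Plasma samples will be collected at the end of each infusion study and banked for future metabolomic analyses". Statistical Plans names four key endpoints (V_CS, V_PC, hepatic glucose production, β-OHB turnover) and says that differences in these "parameters (within the same individuals) for saline vs. glucagon treatment will be assessed by paired t-tests". It names no time point, window or averaging rule.

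**The concern.** A paired t-test needs one number per subject per condition, and the plan does not say which samples produce it. The timing text also allows two readings. The words placing the study after a 3 h infusion could mean that tracers start once glucagon has stopped. In that case a flux sample at the end of the tracers would be taken 180 min after glucagon ended. Alternatively, the infusions run together, and the same sample is taken at 0 min. The 0700 clock time does not settle it. Read literally, it would put the start of the 3 h infusion at about 0400, but it could equally mark the start of the study.

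Even with both infusions running together, a tracer started alongside glucagon needs time to register a change in flux, so an early or very wide window would understate the effect. If several samples exist and the window is chosen after the data are seen, the result for V_CS and the other three endpoints could be steered. With 12 pairs there is little room for a diluted effect. At an assumed two-sided alpha of 0.05, 80% power needs a paired difference of about 0.89 SD. Were only 75% of that captured with the SD unchanged, power would be about 56%.

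**Working it through.** **Which reading fits the text.** The two infusions have equal durations, one antecubital line serves the infusions, and a single baseline draw precedes the tracers. All three fit infusions run side by side and read at the end. So does the Hypothesis section, where all three hypotheses concern the effect of a raised plasma glucagon. Tracing for three hours after glucagon had stopped would be an odd test of them. The document does not state this outright, and the actual schedule is for the sponsor to confirm.

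**How much the window matters on that reading.** Only glucose production can be worked, because only its tracer has both a prime and a rate.

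- Inputs from Study Design/Clinical Plan: prime P = 42 mg/m², rate F = 0.84 mg/m²/min.
- P/F = 42/0.84 = 50 min. Enrichment is flat from time 0 on saline only if fractional turnover k = 1/50 = 2%/min, so this is the turnover that the prime implies.
- Assumptions: one mixed glucose pool Q of constant size; a true rise x in glucose production, complete at tracer start; rate read from the steady-state formula.
- With k′ = k(1 + x) and Ra′ = k′Q, enrichment is E(t) = F/Ra′ + (P/Q − F/Ra′)·exp(−k′t). The apparent rate is F/E(t), compared with the same calculation on saline.

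Example with x = 30%, t = 180 min, Q set to 1:

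- Plateau: 0.84/0.026 = 32.31.
- Remaining transient: (42 − 32.31)·exp(−4.68) = 9.69 × 0.0093 = 0.09.
- E = 32.40, so the apparent rate is 0.84/32.40 = 0.02593, against 0.84/42 = 0.02 on saline.
- Apparent rise 29.6%, which is 98.8% of the true 30%.

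Share of the true rise that shows, for x from 10% to 50%:

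| Window | k = 1%/min | k = 2%/min (implied by prime) | k = 3%/min |
|---|---|---|---|
| 0–180 min mean | 44–47% | 74–78% | 89–92% |
| 120–180 min mean | 69–73% | 96–98% | about 101% |
| 150–180 min mean | 73–77% | 97–99% | about 101% |
| 180 min point | 76–80% | 98–99% | about 101% |

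At the implied turnover, moving from the 120–180 min mean to the final sample changes the share from 95.7% to 97.9% for a 10% rise (2.2 points), and from 98.1% to 99.3% for a 50% rise (1.2 points). The 1%/min and 3%/min columns use assumed turnovers that the document does not give. At 1%/min the late windows differ by about 6.5 points, but even the final sample shows only 76–80%. Most of that shortfall comes from a prime that does not match the pool, and defining a window would not remove it.

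**V_CS, V_PC and β-OHB turnover.** The lactate and β-OHB tracers are given without a prime, and no turnover is stated for them. No corresponding figure can be derived.

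**The case for a change.** The strongest case for a change is that this is the only protocol and statistical plan available, and that its statistical section asks for primary hypothesis testing yet leaves the analysed quantity undefined. The cited methods papers may describe sampling, but the plan does not say that it adopts their window. The lactate tracer is said to give relative rates of V_PC to V_CS, while the tests are on absolute rates; how one becomes the other, and from which samples, is not written down. Fixing a value in advance would close off any choice after the data are seen.

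The omission stands, and so does the point about the ratio. What does not stand is a demonstrated consequence. The schedule is worded identically for both conditions, so the gap does not by itself bias one against the other. The risk of a selected window presupposes several flux samples, and the document does not say how many are drawn; with one sample at the end there is nothing to select. The fall in power to 56% needs a loss of the size produced by averaging from tracer start. The worked figures concern glucose production, which is third among the key endpoints and absent from the numbered hypotheses. A formal check for flat enrichment might also need samples that are not planned, so a remedy of that kind could not be called free.

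**Conclusion.** No change to the plan is called for. The document is a concept form that asks for a concise overview, describes the procedure in brief, and refers measurement to published methods and to a protocol approved by the institution's review committee. Alignment of the infusions and the flux sampling times are operating details left out at that level. That limits what their absence proves, although it does not show that they are settled elsewhere.

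On the reading that fits the text best, an analyst would take the flux values late in the infusion and apply the same rule to both conditions. At the turnover implied by the glucose prime, any such rule shows about 96–99% of a true 10–50% rise in glucose production, and late rules differ by about 1–2 percentage points. This rests on a single mixed pool, a rise complete at tracer start, the steady-state formula and a turnover of 2%/min; at an assumed 1%/min the late windows show 69–80%. The effect on V_CS is unknown and cannot be obtained from the document. Writing down the timeline and the value entering each test would be tidy, but it would record what the analysts would sensibly do anyway.

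### β-OHB turnover is read from m+0 and m+4 only while [3-¹³C]lactate is co-infused, so endogenous β-OHB carrying lactate label falls outside the ratio

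*Combined protocol and SAP*

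**What the plan says.** All the relevant text on measurement is under Study Design/Clinical Plan.

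- The GC/MS paragraph states that β-OHB "enrichment will be measured by GC-MS (CI mode, m/z 257 [m+0] and 261 [m+4". It names no ion between these two and gives no enrichment or turnover equation.
- The PINTA paragraph puts the tracers together: "After collection of baseline blood samples a 3h infusion of tracers as described below will be started". The list that follows starts with lactate ("Relative rates of V_{PC}/V_{CS} will be assessed using a constant" infusion of the 3-¹³C form, at 8.7 µmol/(kg·min)), then a deuterated glucose tracer, then [¹³C₄]β-OHB at 10 µg/(kg·min), 99% APE. One simultaneous infusion is the natural reading.
- The β-OHB method is also referred to a cited publication, which is not part of the documents.

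The result is used in two places. The third item under Hypothesis reads "A physiological increase in plasma glucagon concentrations will promote a significant increase in rates of" β-OHB turnover, which the plan equates with hepatic ketogenesis. Statistical Plans lists "rates of hepatic β-OHB turnover" as the fourth key endpoint, and these "parameters (within the same individuals) for saline vs. glucagon treatment will be assessed by paired t-tests". Background and Rationale also describes β-OHB turnover as a surrogate for hepatic acetyl-CoA content.

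**The concern.** A dilution measurement needs every endogenous molecule counted as tracee. Lactate labelled at carbon 3 becomes pyruvate labelled at carbon 3, and pyruvate dehydrogenase turns that into acetyl-CoA with one ¹³C. Two acetyl-CoA units make one β-OHB, so some newly made β-OHB has one or two labelled carbons. It is endogenous product, but it appears at neither m+0 nor m+4. With only those two ions, enrichment is read too high and turnover too low.

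The baseline blood sample does not solve this. It is drawn before the tracers start, so it can correct for natural abundance but not for label that arrives from lactate during the infusion. The plan mentions no lactate-only check.

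What is at stake is the saline-versus-glucagon comparison for Hypothesis 3. The lost fraction depends on how much of the ketogenic acetyl-CoA comes from labelled pyruvate. Under Objectives the plan reports that, in rodents, glucagon stimulates intrahepatic lipolysis and raises hepatic acetyl-CoA. More fat-derived acetyl-CoA would dilute the pyruvate-derived part, so the loss could be smaller under glucagon than under saline.

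**Working it through.** The plan states no β-OHB turnover, SD or expected effect, so there is no figure of its own to reproduce.

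**1. Do the named ions retain the labelled carbons?** The butyl ester, trifluoroacetyl derivative of β-OHB is C₁₀H₁₅F₃O₄. Its [M+H]⁺ is 257.10, and 261.11 with four ¹³C. The two stated ions are therefore right, all four β-OHB carbons are in the ion, and endogenous m+1 and m+2 fall at 258 and 259.

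**2. Formula for the error.** Let F be the tracer infusion rate.
- Turnover: Ra = F × (1/E − 1).
- With E = m4/(m0 + m4), this is Ra(apparent) = F × m0/m4.
- Let a be the labelled fraction of ketogenic acetyl-CoA. If the two units are drawn independently from one pool, endogenous β-OHB is (1−a)² at m+0, 2a(1−a) at m+1 and a² at m+2. None is taken to reach m+4.
- Hence Ra(apparent) = Ra(true) × (1−a)².

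Example with an assumed true Ra of 5 µmol/(kg·min) and a = 5%: the two-ion reading is 5 × 0.95² = 4.51, which is 9.75% too low. Counting m+0, m+1 and m+2 returns 5.00.

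**3. Range for a.** The documents give none. Assume a = e × f, with pyruvate enrichment e of 20% to 50% and pyruvate share of ketogenic acetyl-CoA f of 2% to 20%. Then a runs from 0.20 × 0.02 = 0.4% to 0.50 × 0.20 = 10%.

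| a | (1−a)² | Error in turnover |
|---|---|---|
| 0.4% | 0.992 | −0.8% |
| 1% | 0.980 | −2.0% |
| 2% | 0.960 | −4.0% |
| 5% | 0.903 | −9.8% |
| 10% | 0.810 | −19% |

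**4. Effect on the comparison.** The true glucagon/saline ratio is multiplied by [(1−a_G)/(1−a_S)]², where S is saline and G is glucagon.

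| a_S | a_G | Multiplier |
|---|---|---|
| any | same | 1.000 |
| 2% | 1% | (0.99/0.98)² = 1.02 |
| 5% | 2.5% | (0.975/0.95)² = 1.05 |
| 10% | 5% | (0.95/0.90)² = 1.11 |
| 3% | 5% | (0.95/0.97)² = 0.96 |

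If a is the same for all subjects and both visits, every paired difference is multiplied by the same (1−a)². The estimate shrinks, but the t statistic does not change.

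**5. What a false ratio could do at n = 12.** Assume a two-sided 5% paired test on the log ratio, with a within-pair SD of 0.1 to 0.2 on that scale (none of this is stated in the plan), and no true effect. A false ratio of 1.02 is significant in 10% (SD 0.1) to 6% (SD 0.2) of trials; a false ratio of 1.05 in 34% to 12%.

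**The case against.** The strongest reply is that the size rests wholly on assumption. Nothing in the documents fixes a or its change under glucagon. At a near 1% the error is about 2% within a condition, and smaller between conditions. This stands.

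Several stronger readings are tempting, and the documents do not support them.

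- A reader might infer that the bias must survive the paired comparison. It does so only if a differs between conditions.
- A reader might infer that a positive Hypothesis 3 result could arise with no change in ketogenesis. That is strained. Suppose the pyruvate-derived flux stays fixed and fat-derived flux alone dilutes it. Lowering f from 20% to 10% then takes fat-derived flux from 4 to 9 units against 1 unit of pyruvate-derived flux, and lowering it from 10% to 5% takes it from 9 to 19. Total acetyl-CoA supply doubles in both cases (5 to 10, 10 to 20). An error of a few percent would then accompany a large change in supply, so exaggeration of a real effect is the more credible risk.
- A reader might take the direction as settled. The supporting premise is rodent data, and the plan also expects glucagon to raise V_PC, so pyruvate handling and e may change too. If a rises, the error works against Hypothesis 3.
- A reader might be struck that the lactate tracer exceeds the β-OHB tracer about 94-fold by moles (8.7/0.0925, taking 10 µg as free acid at 108.09 g/mol) or 113-fold (8.7/0.0769, as sodium salt at 130.0). That ratio does not measure the bias, which depends on e × f.

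It can also be said that this is a concept form asking for a concise overview, and that the cited method may acquire more ions. That is possible and cannot be checked here. The current text names two ions and no equation, so the request to state both remains fair.

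**Conclusion.** The gap is real but of uncertain size. With the two ions named and lactate co-infused, turnover is understated by the factor (1−a)²: about 0.8% to 19% for assumed a of 0.4% to 10%. An equal a in both conditions leaves the glucagon/saline ratio correct. An unequal a biases it, by roughly 2% to 5% upward in the moderate examples of a falling and about 4% downward if a rises from 3% to 5%. A fall is plausible on the plan's premise and would exaggerate an effect in the direction of Hypothesis 3, but the documents do not show that it occurs.

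The conclusion assumes simultaneous infusion, a single acetyl-CoA pool, and turnover calculated from the two named ions. It concerns the last-ranked hypothesis and the fourth key endpoint. Nothing in the plan feeds β-OHB turnover into V_CS, the endpoint behind the sample size, and the link to hepatic acetyl-CoA is a matter of interpretation only. Cheap improvement, low priority.

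**What to change.** In the GC/MS paragraph:

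- Acquire m/z 258 and 259 together with 257 and 261 in the same injection, and 260 as a check on tracer purity.
- Correct for natural abundance with the pre-tracer baseline sample of the same visit.
- State the enrichment and turnover equations, with m+0, m+1 and m+2 as tracee.
- Handle m+3 through the measured isotopologue pattern of the infusate, and do not count it automatically as tracee. If 99% applies to each carbon independently, 0.99⁴ = 96.1% of tracer is m+4 and 4 × 0.01 × 0.99³ = 3.9% is m+3.
- Report m+1 and m+2 by condition. This shows directly whether lactate labelling is large enough to matter and whether it differs between saline and glucagon.

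The cost is three more ions, slightly shorter dwell time per ion, a revised formula and a little more analysis work. No extra blood, visits or staff are needed. If only two ions are acquired, the omission can be repaired later only by re-injecting retained sample.
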